## **6、Possible risks and preventive measures**

During the study, if the patient had poor defecation, Kaisailu could be used to record the date and time of use.

## **7、Statistical Analysis Plan**

The results of the questionnaire filled out by the patients were collected and statistically analyzed, and the scores of constipation symptoms and PAC-QOL (patient assessment of constipation quality of life questionnaire) were tested by paired t-test. The higher the score, the more serious the constipation symptoms, and the lower the score means the relief of constipation symptoms. The minimum score of the scale is 0, the maximum score is 30, and a score of more than 15 can be regarded as constipation. The PAC-QOL is a specific scale for assessing the quality of life of patients with chronic constipation. The PAC-QOL consists of 28 items divided into four dimensions: worries and concerns (11 items), physical discomfort (4 items), psychological discomfort (8 items), and satisfaction (5 items). Each item was scored on a 5-point scale, and the more severe the illness, the higher the score.

The experimental data are expressed in the form of mean  $\pm$  standard error (mean  $\pm$  SD). The difference of intestinal flora was analyzed by Wilcoxon paired test, and it was considered that the data had significant difference. Statistical analysis uses GraphPad Prism and R (version 4.1.2, <https://www.r-project.org/>).

Macrogenomic data were analysed using the bioBakery 3 process to obtain microbial species abundance, gene abundance and metabolic function abundance results.

(1) Data quality control: firstly, the quality of sequencing raw data was checked by FastQC software, then Trimmomatic software was used to excise junctions, low-quality bases and filter low-quality sequences, and then host-sequence comparisons were performed by Bowtie2 to remove host sequence contamination in the sequencing data, and then finally, sequence quality test to confirm that the sequence quality had met the analysis standard.

2) Species annotation: Species annotation was performed using MetaPhlAn software, and the sequences after quality control were compared to the marker gene database using Bowtie2 to obtain the microbial community composition.

3) Gene annotation: select all the microbial genomes that have been detected by MetaPhlAn 3.0, construct the ChocoPhlAn pan-genome database, compare the sequences after quality control to the ChocoPhlAn pan-genome database by Bowtie2 to obtain the gene annotation information of all the known species, and then compare the sequences that have not been compared to the ChocoPhlAn pan-genome database by Diamond. ChocoPhlAn pan-genome by Diamond, and then translated and aligned the sequences not aligned to ChocoPhlAn pan-genome to the UniRef90 protein database, to obtain the gene annotation information of unknown species.

4) Functional annotation: according to the gene annotation results, the ko gene family was corresponded to the KEGG database to obtain the metabolic function annotation information.

5) Visual analysis: according to the species abundance table, gene abundance table and metabolic pathway abundance table of each sample, analyse the  $\alpha$ -diversity and  $\beta$ -diversity of each period, and carry out the difference between groups Anosim, Wilcoxon analysis.

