In our previous analysis, stool microorganisms of 20 constipation patients and 20 healthy people were found to be very different in structure. The difference analysis indicated that *Ruminococcus* was abundant in healthy people. A classification model of AUROC 0.967 was established using Lasso algorithm, and important features of the classification model were as follows: *Ruminococcus* is the feature with the highest weight. SPINGO notes that the genus *Ruminococcus* contains species, in which *Ruminococcus bromii* has the highest relative abundance. A search of data from the GMrepo database revealed that *Ruminococcus bromii* were found in 28,796 trials, belonging to 93 phenotypes. A total of 40,795 valid runs belonged to these phenotypes. The relative abundance of *Ruminococcus bromii* in healthy people is significantly higher than that in constipated people. Therefore, the purpose of this clinical trial is to supplement resistant starch for constipation patients with low abundance *Ruminococcus bromii*, and (1) Observe whether the symptoms of constipation patients are improved; (2) To analyze the changes of intestinal microbes in patients with constipation; (3) Verify whether the relative abundance of *Ruminococcus bromii* increases and analyze the correlation between the relative abundance of *R. bromii* in intestine and the improvement of constipation symptoms in patients with constipation..

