## **3.Research and design**

This study was a non-randomized controlled study without placebo. A total of 30 patients with functional constipation were recruited.

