## 5. Research process

For recruited patients with functional constipation, stool samples were first collected and 2 sachets of resistant starch were administered per day, each pack being 10 g. This could be divided into 2 doses or 2 packs could be taken at a time. The resistant starch was brewed in 200 ml of warm water. The administration was continued for 14 days, in which fecal samples were collected from the volunteers on day 0, day 7 and day 14. On day 0 and day 14 patients filled out the questionnaire which is shown in the attached table.

A questionnaire was used to find out whether the symptoms of the constipated patients improved, while stool samples were collected and analysed by macrogenomic sequencing to investigate what changes occurred in the gut microbes of the patients before and after the resistant starch intervention, with a special focus on whether there was an increase in the relative abundance of *Ruminococcus bromii*. The study was conducted without recruitment advertisements and the recruitment of subjects was completely voluntary, with informed consent signed by the subjects after explaining the possible risks involved in the trial and obtaining their consent to join the study. Volunteers who agreed to join the trial were given a questionnaire to obtain their gut health and other health conditions, and were screened according to the above criteria for selection and exclusion of study participants. The samples collected are named with a number, which does not reveal the subject's personal information, and the subject's identity is kept confidential throughout the study, with only the number and disease phenotype visible. Subjects can withdraw from the study at any stage.

In this study, the composition and structure of the intestinal flora of the subjects will be analyzed, and the subjects can keep abreast of the progress of the test and analysis and obtain their own relevant data. The resistant starch used in this study (HiMaize260) is produced by Ingredion. HI-MAIZE®260 resistant starch is a dietary fiber derived from Ingredion's proprietary high-amylose corn starch that enhances the nutritional content of everyday foods such as white bread, muffins, cookies, cakes and pasta.

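### Section 7 summarises R. bromii abundance as mean ±, which does not match its paired Wilcoxon test and does not show how many of the 30 patients carry the species

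*Combined protocol and SAP*

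**What the plan says.** Section 5 (Research process) singles out one species: the sequencing is done "with a special focus on whether there was an increase in the relative abundance of" R. bromii. Section 2 makes the same question part of aim (3).

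Section 7 (Statistical Analysis Plan) covers the analysis in two statements. On summary: "The experimental data are expressed in the form of mean", followed by a ± term that is labelled both standard error and SD. On testing: "The difference of intestinal flora was analyzed by Wilcoxon paired test". The later list of bioinformatic steps applies the test to the species, gene and pathway abundance tables: "carry out the difference between groups Anosim, Wilcoxon analysis".

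Section 7 does not give:
- the scale on which the flora test is run, or the pair of visits compared (stool is collected on days 0, 7 and 14);
- a rule for patients with zero abundance at one or both visits;
- a median, a paired change or a confidence interval;
- a count of patients in whom R. bromii is detected.

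Section 3 gives the size: "A total of 30 patients with functional constipation were recruited". All of them take resistant starch and no control arm is described, so the comparison is within patients.

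**The concern.** Species relative abundance is usually right-skewed with zeros, and the protocol's own rationale makes both likely here. Section 1 describes the target as patients with low R. bromii, says that some people do not respond to resistant starch, and reports wide variation in the butyrate response.

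With such data the mean follows the few patients with the most of the species, while the signed-rank test uses the ranks of all non-zero paired differences. The report would pair a p-value with a size that describes something else, and the two can point in different directions.

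The denominator is also unseen. A patient with no R. bromii at either visit has a difference of exactly zero. The classical signed-rank test drops such pairs, and nothing in the plan requires the number of remaining pairs to be shown. A claim that R. bromii increased could rest on a small subset of the 30. Aim (3) goes on to correlate abundance with symptom improvement, so a reader needs both the size and the denominator.

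**Working it through.** The plan states no power, SD, effect size or carrier rate, so there is no planned figure to reproduce. The sizes below rest on assumptions.

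**Inputs**
- n = 30 (Section 3).
- Two-sided 5% level: assumed, because Section 7 names none.
- Carriers, 71%: assumed. Section 1 says R. bromii "were found in 28,796 trials, belonging to 93 phenotypes. A total of 40,795 valid runs belonged to these phenotypes". If trials means runs, 28,796/40,795 = 70.6%, so 30 × 29.4% = 8.8, or about 9 non-carriers and 21 carriers. The counts span 93 phenotypes and are not a carrier rate in constipation.
- Log-normal abundance in carriers, natural-log SD 1.3 between patients and 0.7 within: assumed, with 1.0/0.5 and 1.5/1.0 as alternatives.

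**1. Skewness of the summary.** The total log variance at one visit is 1.3² + 0.7² = 2.18. For a log-normal variable SD/mean = √(exp(2.18) − 1) = √7.85 = 2.8, among carriers alone. In simulated samples of 30 the SD exceeds the mean in over 99%, so mean minus SD is negative. The top three patients supply about 58% of the day-0 mean.

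**2. Reported size when nothing changes.** Simulated 95% range of mean(day 14)/mean(day 0) under no true change:
- SDs 1.3/0.7: about 0.45 to 2.2. About a quarter of the non-significant results (25% to 26%) still show a 1.5-fold or larger move.
- SDs 1.0/0.5: 0.62 to 1.61.
- SDs 1.5/1.0: 0.27 to 3.37.

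**3. The same for a paired fold change.** The Hodges-Lehmann fold change under 1.3/0.7 ranges from about 0.65 to 1.53 in simulation. A hand check uses the mean log ratio in 21 carriers: SE = 0.7 × √2/√21 = 0.216, and exp(±1.96 × 0.216) = 0.65 to 1.53. The same formula gives 0.74 to 1.35 for a within-patient SD of 0.5, and 0.55 to 1.83 for 1.0. The between-patient SD cancels in a paired ratio but not in a ratio of means.

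**4. A different model.** With log10 SDs of 0.3 to 1.0 between patients and 0.4 within, a true doubling, and 0%, 30% or 50% non-carriers, the three largest of the 30 changes make up 44% to 83% of the total absolute change. With near-identical carriers they still make up 35% to 38%.

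**5. Denominator.** With 30% or 50% of patients undetected at both visits, about 21 or 15 of the 30 pairs enter the test. At the extreme, six carriers who all rise give an exact p of 2/2⁶ = 2/64 = 0.031, with 24 patients never carrying the species.

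**6. Validity and power of the test.** Type I error of the signed-rank test on untransformed differences is 4.5% to 5.5%. Power, untransformed versus log:
- every carrier doubles: 72% versus 83%;
- a random half double: 24% versus 28%;
- only carriers above the median double (detection limit 0.01%): 36% versus 28%.

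The log scale is ahead in the first two cases and behind in the third.

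**The case against.** The strongest reply is that the planned test is sound and the rest is reporting detail. Much of that stands.

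- A reader might infer that the plan loses power by not taking logs. The documents do not support this. The log scale gains when every carrier rises by the same factor, but Section 1 expects non-responders, and the ordering reverses when only high-abundance carriers respond.
- A reader might infer that the test ranks patients by starting abundance. It ranks absolute change in percentage points. That correlates with baseline, but it is a legitimate target for an aim about relative abundance. Fold change is another choice of estimand, not the correction of an error.
- A reader might infer that dropping non-carriers weakens the test, or that logs would keep them. Pairs at zero on both days carry no information on direction. Pratt handling, which keeps zeros in the ranking, changes power by about 2 points at most. With a fixed pseudo-count their log ratio is also exactly zero, so the six-carrier example gives the same p of 0.031. Only the counts make these patients visible.
- An untransformed scale is inferred from silence, and no sentence ties the mean specifically to the change in R. bromii. The statement does cover all experimental data, and no other flora summary is given.
- Fold change has its own weakness. With a detection limit of 0.1% and about three patients switching detection status, under a true doubling, moving the pseudo-count from 1/2 to 1/100 of the limit moved the upper 97.5th percentile of the Hodges-Lehmann fold change from 3.2 to 10.3.

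None of this defends mean ± as the only summary, or the missing counts.

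**Conclusion.** The concern holds as a mismatch between summary and test, with an unreported denominator. It is not a fault in the test. Under the stated assumptions about 58% of the day-0 mean comes from three of the 30 patients, and with no true change the ratio of means can plausibly read anywhere from a halving to a doubling. A paired fold change among carriers narrows that to about 0.65 to 1.5, which is better but still wide at this sample size. The amounts depend on SDs and a carrier rate that the documents do not give. Across the settings tried, a few patients carried a large share of the change even when carriers were nearly alike (35% to 38% from three).

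The comparison in step 3 is for fold change. A Hodges-Lehmann change in percentage points is not on that scale. Its merit is that it estimates what the signed-rank test on differences tests. This is a cheap improvement that changes what aim (3) can conclude.

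**What to change.** In Section 7, for flora only:

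1. State the scale of the paired Wilcoxon test, the pair of visits and the handling of zero differences before the data are analysed.
2. Replace mean ± with the median (IQR) at each visit and the Hodges-Lehmann paired change with its 95% CI, on the same scale and the same pairs as the test.
3. Tabulate patients absent at both visits, newly detected, lost, up and down, and the number of pairs that entered the test, so that any claim of an increase carries its denominator.
4. If fold change is wanted, give the log fold change as a supportive analysis with one fixed pseudo-count and one sensitivity value.

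The questionnaire scores need no change on this account. The cost is SAP wording and a few lines of R, which Section 7 already names, on the same samples. The downsides are slightly more reporting and, where fold change is shown, its dependence on the pseudo-count.

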Food rich in anti-digestible starch has many functions, such as controlling body weight, reducing blood lipids and blood sugar, regulating intestinal flora and so on, which has attracted the interest of many scholars and become a new field of international food research in recent years. Resistant starch (RS) is the anti-digestion part of compound polysaccharide starch. According to the conditions of enzymatic hydrolysis resistance and starch source, the digestible resistant starch was mainly divided into four types, namely RS1, RS2, RS3 and RS4. From the cause of resistance, RS1 and RS2 have natural resistance to amylase, and the resistance can disappear after gelatinization, while the resistance of RS3 and RS4 is formed by the transformation of starch in the process of food processing or food production. RS1 can coexist with RS2 or RS3 in the same kind of food, and the existence of RS4 can increase the food intake of RS3. Only a small part of the indigestible starch can be digested and absorbed in the small intestine, providing a very low utilization rate of glucose. When most of the rest of the undigested starch enters the colon, it is fermented by the intestinal microflora, mainly producing short-chain fatty acids (SCFAs): acetate, propionate and butyrate. Although both acetate and propionate have health effects, butyrate is particularly thought to improve health and is the fatty acid with the largest increase in resistant starch intake. Butyrate plays an important role in human intestinal health, including reducing inflammation, reducing the risk of colon cancer and improving intestinal barrier function. *In vivo* and *in vitro*, resistant starch diet and butyrate significantly increased the proportion of ChAT immunoreactive intermuscular neurons, intestinal neurons expressed monocarboxylic acid transporter 2 (MCT2), small interference with RNA silenced MCT2, and prevented butyrate-induced increase in the proportion of ChAT immunoreactive neurons. Butyrate and trichostatin A increased the acetylation of histone H3 in intestinal neurons. Src signal pathway inhibitors blocked the effect of butyrate. Resistant starch diet increased colonic transport, and butyrate increased cholinergic-mediated contraction of colonic circular muscles *in vitro*. Although resistant starch has been shown to be one of the best fibers to raise butyrate levels in the population, it is clear that not everyone can get the same benefits, and some people do not respond to resistant starch

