
supplements. This suggests that differences in individual microflora play an important role in determining the outcome of resistant starch consumption, and we need to explore more deeply the mechanism of resistant starch digestion and how it leads to the production of butyrate. In addition, more work needs to be done to understand the effects beyond butyrate levels that may affect health through resistant starch consumption.

Due to the complex structure of resistant starch, some bacteria are needed to initiate the degradation of this semi-crystalline material. *Ruminococcus bromii* and *Bifidobacterium adolescence* are the two known human intestinal microorganisms with the ability to degrade resistant starch. *Ruminococcus bromii* has attracted attention because of its role as a key species in resistant starch metabolism, feeding and / or enabling other members of the intestinal microbiome to obtain the substrate. The amylolytic enzyme of *Ruminococcus bromii* has a unique tissue structure and forms a multi-enzyme complex. Through the adhesion protein and dockerin module, it is attached to the cell surface through the scaffold protein in the cellulose body, so it is called amylosome. This system has been found in a variety of human *Ruminococcus*, and the key enzyme structure of its amylase is highly conserved among strains. Despite its incredible ability to degrade resistant starch, *Ruminococcus bromii* itself does not seem to win or dominate other species in the competition, but plays a beneficial role by cross-feeding other species by releasing sugars and acetates of different lengths. Resistant starch supplementation increased fecal butyrate concentrations in healthy young adults from 8 to 12 mmol/kg wet feces, but responses varied widely between individuals. A follow-up study by the same team found that people with increased *Ruminococcus bromii* abundance in the microbiome were more likely to have a higher butyrate response to potato starch, the results showed that the correct combination of primary degrading bacteria and resistant starch was needed to increase the yield of butyrate.

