## **2.The purpose of the study**

In this study, a group of patients with functional constipation were recruited to take resistant starch: (1) to observe whether the symptoms of patients with constipation improved; (2) to analyze the changes of intestinal microorganisms in patients with constipation; (3) to verify whether the relative abundance of *Ruminococcus bromii* increased and analyze the correlation between the relative abundance of *R. bromii* in intestine and the improvement of constipation symptoms in patients with constipation.

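### ANOSIM is named for comparing repeated samples of the same patients with no within-patient permutation; in its ordinary form it is conservative and can miss small to moderate community shifts

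*Combined protocol and SAP*

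**What the plan says.** Section 3 states that "A total of 30 patients with functional constipation were recruited". It calls the study controlled, but no second arm is described anywhere. Section 5 says that "fecal samples were collected from the volunteers on day 0, day 7 and day 14".

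Section 7, item 5 (Visual analysis), takes the alpha- and beta-diversity "of each period, and carry out the difference between groups Anosim, Wilcoxon analysis". It gives no patient stratum, distance measure or number of permutations, and it does not define the groups. Elsewhere in section 7, pairing is stated for the t-test on the questionnaire scores and for the single-feature comparison: "The difference of intestinal flora was analyzed by Wilcoxon paired test". Nothing equivalent is said for ANOSIM. No significance level is stated.

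Purpose (2) in section 2 is "to analyze the changes of intestinal microorganisms in patients with constipation".

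**The concern.** With one cohort, the only groups available to item 5 are the sampling days. That is an inference from the design, but no other reading is open. The samples compared are therefore not independent, since each patient contributes one to every period.

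Ordinary ANOSIM treats samples as exchangeable and permutes labels freely. A patient's own samples always carry different period labels, so if they resemble each other, those close pairs all fall in the between-period set. This pulls R below zero when nothing has shifted, while the free-permutation reference stays centred on zero and is too wide. The result is too few rejections, not too many.

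ANOSIM is the named test that compares whole communities. If it is run unrestricted, a non-significant result would be weak evidence on purpose (2), because stable differences between people could hide a shift.

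**Working it through.** The plan gives no power or sample-size figure for this analysis, so there is none to reproduce.

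**Step 1: direction, by hand.** R = (mean between-period rank − mean within-period rank)/(M/2), with M = N(N−1)/2.

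- Two periods: N = 60, M = 1,770, M/2 = 885. Between-period pairs: 30 × 30 = 900, of which 30 join a patient to himself or herself. Within-period pairs: 2 × 435 = 870.
- Limiting case: the 30 same-patient pairs hold ranks 1 to 30 (mean 15.5), and all other pairs average (31 + 1,770)/2 = 900.5.
- Between-period mean = (30 × 15.5 + 870 × 900.5)/900 = 871.0. R = (871.0 − 900.5)/885 = −0.033 with no shift at all.

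The simulated mean R with no shift moves from 0.000 to −0.033 as within-patient likeness rises, which agrees.

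**Step 2: size, by simulation.** From the documents: 30 patients and two or three of the three sampling days. Everything else is assumed:

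- 100 log-normal taxa (SD of taxon means 1.5), 10 of them shifted in every patient
- Bray-Curtis distance and the 5% level
- with three periods, half the shift present at day 7 and all of it at day 14
- 199 permutations and 1,000 trials per setting, so the Monte Carlo SE is at most √(0.5 × 0.5/1,000) = 1.6 points

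Between-patient share = b²/(b² + w²), where b/w is the between/within-patient SD: 0/1, 0.33/1, 0.65/1, 1/1, 1.5/1 and 1.5/0.7. For example, 1.5²/(1.5² + 0.7²) = 2.25/2.74 = 0.82.

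Rejection rates in %, unrestricted v within-patient:

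| Share | No shift, 2 periods | No shift, 3 | 1 log, 2 periods | 1 log, 3 | 1.5 log, 2 periods | 1.5 log, 3 |
|---|---|---|---|---|---|---|
| 0 | 5.3 v 5.5 | 3.9 v 4.2 | 84.9 v 84.8 | 73.6 v 73.2 | 99.1 v 99.1 | 97.8 v 97.9 |
| 0.1 | 2.4 v 4.3 | 2.2 v 4.7 | 79.6 v 83.9 | 62.4 v 72.4 | 98.6 v 99.1 | 96.2 v 98.0 |
| 0.3 | 0.6 v 4.3 | 0.4 v 3.8 | 58.5 v 82.4 | 28.7 v 68.6 | 95.9 v 99.2 | 87.0 v 97.8 |
| 0.5 | 0 v 4.7 | 0 v 6.0 | 24.2 v 75.4 | 5.9 v 61.2 | 83.4 v 98.9 | 57.2 v 96.0 |
| 0.69 | 0 v 3.6 | 0 v 5.8 | 3.5 v 69.7 | 0.2 v 53.5 | 43.3 v 97.5 | 9.8 v 94.8 |
| 0.82 | 0 v 4.8 | 0 v 6.5 | 2.4 v 91.4 | 0 v 81.7 | 60.7 v 99.9 | 14.3 v 99.4 |

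**Step 3: non-responders.** The background says that "not everyone can get the same benefits, and some people do not respond to resistant starch". If half respond (assumed), power at 1 log is:

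- shares 0.1-0.3: 7-17% v 23-24% (two periods), 2-10% v 16-18% (three)
- shares 0.5-0.82: 0-1% v 17-29%, 0% v 15-23%

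**Step 4: a second model.** This used 40 taxa, 4 shifted, shifts in units of total log-scale SD, two periods and 99 permutations.

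- Unrestricted type I error: 0.056, 0.004, 0.000 and 0.000 at correlations 0, 0.3, 0.5 and 0.7; within-patient 0.048-0.066.
- Power at correlation 0.5: 0.08 v 0.62 at 0.5 SD, 0.63 v 0.98 at 0.75 SD, 0.97 v 1.00 at 1.0 SD.
- In a variant with randomly drawn taxon means, both schemes did badly in some settings (correlation 0.5, 0.75 SD: 0.00 v 0.16).

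The direction is the same throughout; the size depends on the assumptions.

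**The case against.** The strongest reply is that this is a gap in specification, not a stated error. The plan does not say that permutation is free, and harm needs both an unrestricted run and a material within-patient correlation. The documents give no such figure. The background says only that "differences in individual microflora play an important role in determining the outcome of resistant starch consumption". That stands, and at zero correlation the two schemes agree.

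The consequence is also limited. The error is conservative, so a significant ANOSIM stands. *R. bromii*, the taxon the plan singles out, is covered by the paired Wilcoxon. Item 5 is headed as visual analysis and carries no decision rule. All of this is fair, and it keeps the point short of essential.

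The size of the loss does depend on the assumptions:

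- With fewer taxa shifted (two periods, 1 log, shares 0.3-0.69), within-patient power drops to about 11% for one taxon, 27% for three and 44-54% for five, against 0-5%, 1-14% and 0-26% unrestricted.
- Total variance is not constant across the table: it is 1 at share 0 and 1.5² + 1² = 3.25 at share 0.69, so a 1-log shift falls from 1 SD to 1/√3.25 = 0.55 SD. With total variance held at 2, two-period power is about 51% v 58% at share 0.1, 35% v 65% at 0.3 and 12% v 98% at 0.82. Part of the collapse to 2-4% therefore reflects a smaller standardised shift, but the gap remains.
- At 1.5 log and shares up to 0.3, two-period unrestricted ANOSIM finds the shift in 96-99% of trials.

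These points change the amount of power lost, not the direction.

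**Conclusion.** The concern holds. ANOSIM is named for samples that are repeated within patient, and no within-patient permutation is stated. Run in its ordinary form, it is conservative in proportion to how alike a patient's samples are. At an assumed 1-log shift in every patient, the two-period power loss runs from nothing at share 0, through about 4 points at 0.1 and 24 at 0.3, to 51-89 points from 0.5 upward. Large shifts are still mostly found at low shares. Type I error is reduced, not inflated.

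Restricting the permutation does not turn a null result into proof of no shift: with half the patients responding, power is at most 29% under either scheme. Confidence in the direction is high. Confidence in the size is moderate at best, because correlation, effect size, number of taxa shifted and distance measure are all assumed. The change should be made. It concerns the whole-community comparison only.

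**What to change.** Add to item 5:

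> Beta-diversity between periods is tested by ANOSIM with permutations of period labels restricted within patient (patient as stratum); the number of patients contributing to each contrast is reported.

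The distance measure, number of permutations, significance level and contrasts (two or three periods) should be fixed in the same place. The Wilcoxon needs no change, since section 7 already calls it paired.

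The cost is one sentence and a permutation setting in R, which the plan already uses; no new data are needed. The downside is missing samples, because "Subjects can withdraw from the study at any stage". A patient with one sample in a contrast adds nothing to the restricted permutation. If 6 of 30 lack one sample (assumed; 1-log shift, shares 0.1-0.82):

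- Two periods: the within-patient test on the other 24 has 56-85% power, 6 to 14 points below that with all 30, against 2-66% for unrestricted ANOSIM on all 60 − 6 = 54 samples.
- Three periods, sample missing at random: 45-71% with the 6 kept and 42-72% without them, against 0-58% unrestricted.
- Three periods, day 14 always missing: 30-59% with the 6 kept and 41-73% without them, against 0-50% unrestricted.

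A patient with two of three samples can be kept in the three-period test, but keeping such patients costs power when day 14 is the missing sample. The rule should be set before the data are seen.

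### ANOSIM is the only whole-community test between periods and has no test of spread beside it, so a significant result cannot separate a common shift from a change in between-patient spread

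*Combined protocol and SAP*

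**What the plan says.** - **Design.** Section 3: "A total of 30 patients with functional constipation were recruited". Section 5: "fecal samples were collected from the volunteers on day 0, day 7 and day 14". Only one treated group is described, so the groups compared in item 5 are the sampling periods.
- **Purpose.** Section 2, purpose (2): "to analyze the changes of intestinal microorganisms in patients with constipation".
- **Whole-community test.** Section 7, item 5 looks at alpha- and beta-diversity by period and then says to "carry out the difference between groups Anosim, Wilcoxon analysis". It names no distance, no permutation scheme and no formal test of dispersion.
- **Other flora test.** Section 7 also states: "The difference of intestinal flora was analyzed by Wilcoxon paired test". That test handles one taxon or index at a time. It tests neither overall composition nor spread.
- **Background.** Section 1 says that "some people do not respond to resistant starch" and, on faecal butyrate in healthy young adults, that "responses varied widely between individuals".

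**The concern.** ANOSIM asks whether samples from different periods are further apart, in ranks, than samples from the same period. That can happen because the flora of most patients moved the same way. It can also happen because patients became more or less alike while the average stayed put. These are different answers to purpose (2), and the second is no evidence of a common effect of the starch. The paired Wilcoxon test cannot resolve it, because it sees one variable at a time. Since the background describes uneven response to resistant starch, a change of spread is a plausible outcome and the plan should be able to recognise it.

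**Working it through.** The plan gives no power, alpha or sample-size figure for this test, so there is nothing to reproduce. The significance level is left open ("it was considered that the data had significant difference"); 0.05 is assumed. Every distribution setting below is an assumption.

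**1. The statistic.** Two periods of 30 samples give 60 × 59 / 2 = 1,770 pairs. Within-period pairs number 2 × (30 × 29 / 2) = 870. Between-period pairs number 30 × 30 = 900, of which 30 join two samples of the same patient. R = (mean rank between − mean rank within) / (1,770 / 2 = 885).

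**2. Why spread matters.** Take p species, no mean difference, and per-species SDs s0 and s14. For different patients, the expected squared distance is 2p·s0² within day 0, 2p·s14² within day 14, and p(s0² + s14²) between them. The last is exactly the mean of the first two. PERMANOVA works on squared distances, so with equal period sizes it has nothing to pick up. ANOSIM works on ranks, which are not linear in squared distance, so this balance is lost. In a 20-dimensional normal model with uncorrelated samples, mean R was 0.002, 0.038 and 0.089 at SD ratios of 1, 1.25 and 1.5.

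**3. Why the permutation scheme matters.** The 30 same-patient pairs count as between-period and tend to be the shortest distances. If they take ranks 1 to 30, the other 1,740 pairs average (31 + 1,770) / 2 = 900.5. The between mean is then (30 × 15.5 + 870 × 900.5) / 900 = 871.0, and R = (871.0 − 900.5) / 885 = −0.033. The simulated mean R with equal spread and within-patient correlation 0.8 was −0.034. Unrestricted permutation breaks up these pairs, so the observed R starts below its reference distribution and small changes of spread are masked. Permuting within patients keeps the pairs together, removes the handicap, and exposes the reaction to spread.

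**4. Size of the spread change.** Between-patient SD 1 and day-to-day SD 0.5 give a baseline variance of 1 + 0.25 = 1.25 and a within-patient correlation of 1 / 1.25 = 0.8. A mean-zero individual response with SD τ on day 14 gives the ratio √((1.25 + τ²) / 1.25):
- τ = 0.5: √1.20 = 1.10
- τ = 0.75: √1.45 = 1.20
- τ = 1.0: √1.80 = 1.34

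**5. Rejection at 0.05 with no common shift.** Euclidean distance on log abundance, 10 to 100 species, 150 to 400 trials per setting, 199 permutations. Ranges cover species numbers and repeated runs.

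| Spread increase | ANOSIM, unrestricted | ANOSIM, within patient | PERMANOVA, within patient | Paired distance to centroid |
|---|---|---|---|---|
| none | 0% | 4-10% | 2-8% | 5-7% |
| 10% | 0% | 17-73% | 2-8% | 59-100% |
| 20% | 0-6% | 59-100% | 2-8% | 97-100% |
| 34% | 17-73% | 97-100% | 2-8% | 100% |

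With 150 trials, the standard error of a 5% rate is √(0.05 × 0.95 / 150) = 1.8 points.

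**6. Sensitivity to correlation.** In the 20-dimensional model (300 trials, 299 permutations) at SD ratio 1.25, unrestricted ANOSIM rejected in 59%, 15% and 3% of trials for within-patient correlations 0, 0.5 and 0.8. Within-patient ANOSIM rejected in 57%, 89% and 96%. At ratio 1.5 both schemes gave 99-100%. Testing three periods together, with spread raised on days 7 and 14 (ratios 1.25 to 2), gave 0-66% unrestricted and 31-97% within patient.

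**7. Bray-Curtis.** Here a mean-zero log response also moves mean proportions, so the tests separate less. Response SD 1.0, between-patient SD 1, both tests permuted within patient, ANOSIM v PERMANOVA:
- 10 species: 24% v 6% in one run, 34% v 16.5% in another
- 60 species: 83% v 48%
- 100 species: 93% v 71% in one run, 80% v 52% in another; both 100% when mean abundances were equal

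Unrestricted ANOSIM with unequal mean abundances gave 0-4% (10 species) and 0-11% (100 species) over response SD 0.5 to 1.0.

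**The case against.** Several points on the other side stand.

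- **The largest rates are not the plan as written.** A reader might infer that the planned analysis gives a misleading signal in nearly every trial with uneven response. The documents do not support that. The high rates at +10% and +20% need permutation restricted within patients, which item 5 does not name. Under unrestricted permutation, strong within-patient correlation hides small changes of spread.
- **The background does not predict wider community spread.** A reader might infer that it does. Its two statements concern benefit and butyrate response, the latter in healthy young adults. Neither reports dispersion of composition or patients moving in opposite directions. A mix of responders and non-responders implies a real average shift: with half responding in one direction, within-patient ANOSIM and PERMANOVA gave similar rates (40% v 52%, 100% v 100%, 71.5% v 79%).
- **The plan does not say it will read ANOSIM as a common shift.** It speaks of a difference and of changes, and altered spread is a change. The gap is that nothing in the plan identifies which kind was found.
- **Beta-diversity by period is analysed.** This may describe within-period dissimilarity, so the accurate statement is that no formal test of spread is named.
- **PERMANOVA is not immune on every distance.** Step 7 shows this for Bray-Curtis, so the remedy must name the distance.

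What remains is that ANOSIM responds to both kinds of change and stands alone as the community test. Adding only within-patient permutation would make the ambiguity show more often.

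**Conclusion.** The point holds as a limit on interpretation. A significant ANOSIM under item 5 cannot by itself separate a common shift of the flora from a change in between-patient spread. A change of spread is plausible from the background but not shown by it.

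The size depends on the permutation scheme. Unrestricted, the effect is negligible up to a spread increase of about 10-20% and material at about 34% (roughly 17-73% rejection with no common shift). Restricted within patients, it appears at +10% (roughly 17-73%) and is near 100% at +34%. These figures assume 30 complete patients, two periods, Euclidean distance on log abundance, within-patient correlation 0.8 and alpha 0.05. With weaker correlation, the unrestricted test reacts to smaller changes of spread.

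The consequence is confined to the whole-community statement. Symptom scores, PAC-QOL and the *R. bromii* comparison do not use ANOSIM. It is a cheap and worthwhile improvement, not a defect that endangers the study.

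**What to change.** In section 7, item 5:

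1. **Name the distance**, for example Euclidean on log-ratio-transformed abundance, with the rule for zero counts. On Euclidean log-scale distances PERMANOVA held 2-8% under mean-zero log responses.
2. **Main community test:** PERMANOVA of period, permuted within patient, on patients with both samples of the pair compared so that the periods are equal in size. Report R².
3. **Test of spread:** each sample's distance to its period centroid, compared pairwise within patient.
4. **Reading rule:** report a common shift only if PERMANOVA supports it. If only the spread changes, report variable response. If Bray-Curtis is used, note that uneven log-scale responses can also move mean proportions, so read a significant PERMANOVA with changed spread cautiously.
5. ANOSIM may stay as a secondary display.

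The cost is a few sentences in the SAP, a few lines of R on the same distance matrix, and one extra test to report. No new data are needed.
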